6.2 INFORMED CONSENT

All participants must sign the informed consent prior to participating in any clinical trial-related procedures. The informed consent documentation must be in compliance with applicable regulations and GCP. Qualified clinical trial personnel will:

- Meet with prospective clinical trial participants
- Explain the clinical trial
- Provide clinical trial participants with an Informed Consent Form (ICF) that includes the following in a language that is understandable to the subject:
 - Screening test(s) description
 - Eligibility criteria for entering the clinical trial
 - Clinical trial treatments and follow-up procedures description
 - Explanation of the clinical trial, including but is not limited to:
 - Clinical trial objectives
 - Potential benefits and risks
 - Discomforts/inconveniences
 - Subject's rights and responsibilities

The subject or subject's legally authorized representative is then requested to sign and date the ICF. A copy of the signed informed consent documentation must be provided to the subject or subject's legally authorized representative. The qualified clinical trial personnel will document the process of obtaining informed consent within the source record. Signed ICFs are maintained in the subject's source records and must be accessible for verification at any time. Signing of the ICF begins the 60 day screening window.

6.3 ASSIGNMENT OF SUBJECT IDENTIFICATION NUMBERS

Each subject who consents will be assigned a unique subject identification number (SID), which identifies the subject for all clinical trial-related procedures. SIDs are a combination of a four digit site code and a four digit subject number starting with 0001. After SIDs are assigned, they cannot be reused or reassigned for any reason. Information regarding the SID and screen date will be documented on a screening and enrollment log/system and in the Case Report Form (CRF).

Participants meeting eligibility criteria listed in the protocol will be randomized by a computer generated allocation schedule.

6.4 SAFETY EVALUATIONS

PHYSICAL EXAM AND TARGETED PHYSICAL ASSESSMENTS

A full physical examination will be conducted during Screening and at study discharge/End of Study visit (i.e., Week 48, Week 68 or any other study discontinuation visit). A targeted physical assessment will be performed at other visits as determined by the Investigator or directed per subject complaints.

VITAL SIGNS

Vital signs including oral temperature, respiration rate, blood pressure and heart rate will be measured at Screening and at select visits during the study.

HEIGHT AND WEIGHT

Weight (kg) and height (cm) will be collected at Screening.

12-LEAD ECG

A single 12-lead ECG will be performed at Screening for all participants to determine eligibility. ECG results obtained within 60 days of Day 0 are acceptable. The ECG should include measurements of ventricular rate, PR, QRS, QT, QTcb or QTcf, as well as an assessment of whether the ECG is normal or abnormal. Abnormal ECGs should be interpreted as clinically significant or not clinically significant. Dosing will be delayed in the event of a clinically significant abnormal pre-dose ECG until it has been reviewed by the PI, qualified PI designee, MM or Sponsor consultant cardiologist and deemed safe to proceed.

LABORATORY EVALUATIONS

At Screening and select visits during the study, blood samples will be collected for safety and immunology assessments. Approximately 250 mL and 240-340 mL of blood will be drawn from each subject in Part 1 and Part 2, respectively, over the course of the study. Participants may be asked to come back for additional blood draws if collected blood sample is lost or unevaluable for any reason.

Hematology [Complete blood count (CBC) with automated differential]:

White blood cell (WBC) count, red blood cell (RBC) count, hemoglobin, hematocrit and platelet count will be measured at Screening and select visits during the study.

Serum chemistry:

Electrolytes [Sodium (Na), Potassium (K), Chloride (Cl), Bicarbonate (HCO3 or CO2), Calcium (Ca), Phosphate (PO4)], glucose, BUN (blood urea nitrogen), and Creatinine (Cr) will be measured at Screening and select visits during the study.

Liver function:

Alanine aminotransferase (ALT) and aspartate aminotransferase (AST) will be measured at Screening and select visits during the study.

Urinalysis:

Urine samples will be tested by dipstick for glucose, protein, and hematuria at Screening and select visits during the study. If abnormal (presence of protein, hematuria, or glucose $\geq 1+$), a microscopic examination should be performed.

Serology:

Antibodies to MERS-CoV (per PI discretion), Hepatitis B surface antigen (HBsAg), Hepatitis C antibody and HIV antibody or rapid test will be measured at Screening only.

Pregnancy Testing:

For women of childbearing potential (WOCBP), a serum pregnancy test will be obtained at Screening and a urine pregnancy test will be performed prior to any dosing. A negative result for urine β -HCG (test must have a sensitivity of at least 25 mIU/mL) must be available prior to each administration of IP. If the β -HCG test is positive, indicating that the participant is pregnant prior to completing the specified dose regimen, then no further IP

will be administered. Every attempt should be made to follow pregnant participants for the remainder of the study and to determine the outcome of the pregnancy.

6.4.1 INJECTION AND EP

Participants in Part 1 Study Groups A, B and C will receive one injection of INO-4700 in a volume of ~0.1 mL by ID injection above an acceptable muscle location for injection, the injection site is assessed for IP leakage, and the injection is followed immediately by EP. Part 1 Study Groups D and E will receive two injections of INO-4700, each in a volume of ~0.1 mL, above an acceptable muscle location on two different limbs, the injection site is assessed for IP leakage, and the injection is followed immediately by EP. Part 1 Study Groups F and G will receive one injection of placebo in a volume of ~0.1 mL by ID injection above an acceptable muscle location for injection, the injection site is assessed for IP leakage, and the injection is followed immediately by EP. Part 1 Study Groups H and I will receive two injections of placebo, each in a volume of ~0.1 mL, above an acceptable muscle location on two different limbs, the injection site is assessed for IP leakage, and the injection is followed immediately by EP.

Participants in Part 2 will receive one or two injections per dosing visit of the optimal dose of INO-4700 or placebo in volume of ~0.1 mL by ID injection above an acceptable skin location for injection, the injection site is assessed for IP leakage, and the injections is followed immediately by EP.

Only if the deltoid muscle is not a suitable location (see exclusion criterion 'h'), the ID injection can then be administered above the lateral quadriceps followed immediately by EP. IP must not be given within 2 cm of a tattoo, scar, keloid, previous injection site at the same dosing visit, or active lesion/rash. Also, ID injection followed immediately by EP must not be performed on the skin of an extremity which has any metal implants or implantable medical device (e.g., surgical rods, pins or joint replacements). If a subject has an implanted cardiac defibrillator or pacemaker, ID injection/EP must not be performed above the deltoid muscle on the same side of the body where the device is located.

6.4.2 MANAGEMENT OF ANXIETY AND PAIN DUE TO ELECTROPORATION (EP) PROCEDURES

Participants may be offered topical anesthetic (e.g., EMLA or equivalent) to prevent discomfort from the injection/EP procedure. If a topical anesthetic is used, an approximate 1.5 cm diameter amount will be applied without occlusion to the administration site ~30 minutes prior to injection/EP.

Participants may be offered a mild sedative (e.g., 0.5-1 mg lorazepam or equivalent) for anxiety related to the injection/EP procedure. Mild sedatives may be administered approximately 1 hour prior to injection/EP on dosing visits. Participants who receive a mild sedative must not be allowed to operate a motor vehicle for 3-4 hours after receiving medication and should have arranged transportation to depart the study site.

In case of pain, participants may be treated with a non-narcotic analgesic (e.g., ibuprofen, ketorolac) after injection/EP.

Participants who are allergic to or have contraindications to EMLA, ibuprofen, ketorolac or a mild sedative may be offered a suitable alternative.

Medication taken for pain management will be documented as concomitant medications.

6.4.3 ASSESSMENT OF LABORATORY ABNORMALITIES

Blood will be drawn for serum chemistry, liver function, and hematology and urinalysis performed at the visits listed in the Schedule of Events (Tables 3, 4 and 5) as listed in [Section 6.4](#).

Laboratory AEs will be assessed and graded in accordance with the “Toxicity Grading Scale for Healthy Adult and Adolescent Volunteers Enrolled in Preventive Vaccine Clinical Trials”, issued in September 2007 ([Appendix A](#)).

6.4.4 ASSESSMENT OF CLINICAL TRIAL ADVERSE EVENTS (AEs)

Participants will be queried regarding the occurrence of any adverse events including adverse events related to injection site reactions, concomitant medications and new onset illness or disease during their study visits. Participants will be reminded to contact study personnel and immediately report any event for the duration of the study. All adverse events will be captured from the time of informed consent until study discharge. These events will be recorded on the subject's CRF.

6.4.5 ASSESSMENT OF INJECTION SITE REACTIONS

The IP administration procedure consists of an ID injection (formation of a wheal) of IP followed by insertion of the ID Array needles (electrodes) through the skin and into the wheal followed by delivery of the electroporation pulses. This procedure is broadly described as administration because it involves more than the injection of a drug. Consequently, reactions arising from the IP administration procedure may be reported as administration site or injection site reactions. When evaluating administration (injection) site reactions throughout the study, it is most important to be as specific as possible by selecting the most appropriate term (see [Table 9](#) below) and use the grading scale as listed in the Toxicity Grading Scale for Healthy Adult and Adolescent Volunteers Enrolled in Preventive Vaccine Clinical Trials, issued September 2007 ([Appendix A](#)). Administration (injection) site reactions and administration site pain will be evaluated starting 30 minutes following injection/EP. In addition, other events associated with administration (injection) site reactions (e.g., hematoma, infection or necrosis) should also be reported with preferred terms specific for administration (injection) site reactions.

Table 9: Grading Scale for Injection Site Reactions

Local Reaction to Injectable Product (Grade)	Mild (1)	Moderate (2)	Severe (3)	Potentially Life Threatening (4)
Pain	Does not interfere with activity	Repeated use of non-narcotic pain reliever >24 hours or interferes with activity	Any use of narcotic pain reliever or prevents daily activity	Emergency room visit or hospitalization
Tenderness	Mild discomfort to touch	Discomfort with movement	Significant discomfort at rest	ER visit or hospitalization
Erythema/Redness ^a	2.5-5 cm	5.1-10 cm	>10 cm	Necrosis or exfoliative dermatitis
Induration/Swelling ^b	2.5-5 cm and no interference w/ activity	5.1-10 cm or interferes with activity	>10 cm or prevents daily activity	Necrosis

September 2007 “FDA Guidance for Industry-Toxicity Grading Scale for Healthy Adult and Adolescent Volunteers Enrolled in Preventive Vaccine Clinical Trials”

^a In addition to grading the measured local reaction at the greatest single diameter, the measurement should be recorded as a continuous variable

^b Should be evaluated and graded using the functional scale as well as the actual measurement.

6.4.6 PERIPHERAL BLOOD IMMUNOGENICITY ASSESSMENTS

Whole blood and serum samples will be obtained to assess overall immune response. Immunology blood and serum samples are to be collected at Screening and select visits during the study. Both Screening and Day 0 immunology samples are required to enable all immunology testing. However, at the Principal Investigator’s discretion, collection of the screening immunology samples may be postponed and collected along with the Day 0 samples. Details of the immunology sample collection and shipment information will be provided in the Laboratory Manual. The T and B cell immune responses to INO-4700 will be measured using assays that include but are not limited to ELISA, neutralization, assessment of immunological gene expression, assessment of immunological protein expression, flow cytometry and ELISPOT.

An immune responder is defined as having either an increase in vaccine antibody titer compared to baseline or an increase in the number of vaccine specific IFN-gamma secreting cells as compared to baseline.

Determination of analysis of collected samples for immunological endpoints will be determined on an ongoing basis throughout the study.

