8.3 STATISTICAL HYPOTHESES

No formal statistical hypothesis will be tested in Part 1 of this trial. The hypothesis in Part 2 of this trial is $H_0: p \leq 70\%$ versus $H_1: p > 70\%$, where p denotes the true population overall immunological response rate for the selected optimal dose of INO-4700.

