8.5.2 PRIMARY IMMUNOGENICITY ANALYSES

For both Part 1 and Part 2, antigen specific binding antibody titers, MERS-CoV neutralizing antibody titers, and specific cellular immune responses will be analyzed by Study Group. Binding antibody titer will be analyzed for each Study Group using the geometric mean and associated 95% confidence intervals. Percent neutralizing antibodies and antigen specific cellular immune response increases will be analyzed for each Study Group using medians, inter-quartile range and 95% confidence intervals. Percentage with overall immune response, inclusive of seroconversion (i.e., positive titer), and corresponding 95% Clopper-Pearson confidence intervals will be analyzed within each Study Group.

In Part 1, the difference in percentage of overall immune responders including seroconverters between all pairs of INO-4700 Study Groups will be calculated along with corresponding exact 95% confidence intervals.

In Part 2, the primary hypothesis of $H_0: p \leq 70\%$ versus $H_1: p > 70\%$ will be tested with an exact test of a binomial proportion. In addition, the binding antibody titer difference between INO-4700 and placebo will be analyzed using the geometric mean fold ratio and associated 95% confidence interval. Percent neutralizing antibodies and antigen specific cellular immune response differences between INO-4700 and placebo will be analyzed using the difference in medians and associated 95% confidence intervals.

All of these primary immunogenicity analyses will be conducted on the participants in the mITT and PP populations.

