8.5.6 INTERIM ANALYSES

No formal interim analyses will be performed for this trial. However, safety and tolerability will be assessed by the DSMB as noted above for the participants in each Study Group.

A Sponsor unblinded review of the week 10 immunogenicity and safety data will be made during Part 1 of this study when all evaluable data observations are available in order to determine the optimal dose for the Part 2 of the study. The selection of the optimal dose for Part 2 will involve consideration of weighted ordered criteria described in [Figure 3](#) below.

Figure 3: Weighted Ordered Dose Selection Criteria

At a minimum, the optimal selected dose will have a 70% overall immune response and acceptable safety profile as determined by the DSMB and Inovio Medical Council. Other criteria listed in [Figure 3](#) will contribute to the selection of the right optimal dose if the overall immune responses and safety profiles are similar between the Study Groups in Part 1.

A group-level unblinded review of the immunogenicity and safety data will be made once week 12 visit data are complete for all participants in Part 2 whilst maintaining subject-level blinding. Long-term follow-up data will continue to be collected for all participants with remaining visits through to the final visit. These summaries and analyses will allow the Sponsor and collaborators to have results with respect to the immunogenicity and safety endpoints up to and including the Part 2 Week 12 visit on which to inform product development goals. No subject-level immunogenicity data will be produced and subject-level immunogenicity data will not be available in the clinical trial database until all other clinical trial data are finalized at the end of the trial. Thus, Part 2 of the trial will remain blinded to the Sponsor and collaborators with respect to subject treatment assignment.

In order to protect the blind, for the group-level unblinded review, no safety analysis will be provided if the total of subjects who experience the event of interest is greater than 0

and the count of these events relative to the total count of events produces a percentage less than 3% for a given analysis.

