Principal Investigator Signature:

Principal Investigator Printed Name (first and last)

Principal Investigator Signature

Date (ddMmmYYYY)

Clinical Trial Site Number: _____

Clinical Trial Site Name: _____

Item 1: Discontinuation of Study into Part 2 and Analysis of Week 48 Samples

The MERS-201 trial will not proceed to Part 2. The decision was made in collaboration between the Study Sponsor, Inovio Pharmaceuticals, Inc. (INOVIO) and the Study Funder, The Coalition for Epidemic Preparedness Innovations (CEPI). The decision was based on the Week 10 interim immunology results, which did not meet the criteria for Part 2 dose selection as outlined in the Protocol Section 8.5.6, for any dose group in Part 1. There were no safety concerns related to the study and Week 10 interim safety results were consistent with the safety results across Inovio's platform for intradermal administration.

Since the study objectives were not met and the study is not moving forward into Part 2, no additional immunology data is needed. Therefore, the Part 1 Week 48 samples will not be analyzed.

Signature Page for VV-TMF-131691 v1.0

Reason for signing: Approved	Name: [REDACTED] Role: Approver Date of signature: 20-Jan-2023 21:27:47 GMT+0000
------------------------------	--

Signature Page for VV-TMF-131691 v1.0

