4.3. Immunology, Safety, and Exploratory Evaluations

4.3.1. Immunology Evaluations

The following immunogenicity analyses will be conducted on participants in the PP and mITT study populations.

In Part 1, the difference in percentage of overall immune responders including seroconverters (i.e. positive titer) between all pairs of INO-4700 study groups will be calculated along with corresponding exact (Clopper-Pearson) 95% CIs. The T and B cell immune responses to INO-4700 will be measured using assays that include ELISA, neutralization, assessment of immunological gene expression, assessment of immunological protein expression, flow cytometry, and ELISPOT.

In Part 2, the primary hypothesis of $H_0: p \leq 70\%$ versus $H_1: p > 70\%$ will be tested with an exact test of a binomial proportion. In addition, the binding antibody titer difference between INO-4700 and placebo will be analyzed using the geometric mean fold ratio and associated 95% confidence interval. Percent neutralizing antibodies and antigen specific cellular immune response differences between INO-4700 and placebo will be analyzed using the difference in medians and associated 95% CIs.

For both Part 1 and Part 2, antigen specific binding antibody titers, MERS-CoV neutralizing antibody titers, antibodies to other coronaviruses, and specific cellular immune responses will

be analyzed by study group and treatment group, respectively. Time to peak post-baseline titers will be summarized using descriptive statistics. Binding antibody titer will be analyzed for each study group using the geometric mean and associated 95% CIs. Percent neutralizing antibodies and antigen specific cellular immune response increases will be analyzed for each study group using medians, inter-quartile range and 95% CIs. Percentage with overall immune response, inclusive of seroconversion and corresponding 95% Clopper-Pearson CIs will be analyzed within each study and treatment group.

All immunologic data will be presented in data listings.

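### The responder rule counts any rise over baseline, with no numeric cut-off in the visible text, and both 70% criteria judge the active-arm rate without reference to placebo

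*Protocol*

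**What the plan says.** Protocol 6.4.6 gives the operative definition: "An immune responder is defined as having either an increase in vaccine antibody titer compared to baseline or an increase" in the number of vaccine-specific IFN-gamma secreting cells, again relative to baseline. The same section lists ELISA and neutralization among an open set of assays and does not say which one supplies the deciding titer.

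Protocol 8.5.2 and SAP 4.3.1 add only that overall response includes seroconversion, glossed as a positive titer. Neither gives a number or an assay.

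The responder rate carries two decisions:
- **Part 1 selection (Protocol 8.5.6).** "At a minimum, the optimal selected dose will have a 70% overall immune response", judged at Week 10: "A Sponsor unblinded review of the week 10 immunogenicity and safety data will be made during Part 1 of this study".
- **Part 2 hypothesis (Protocol 8.3, 8.5.2; SAP 4.3.1).** H0: p ≤ 70% against H1: p > 70%, by an exact binomial test, where p "denotes the true population overall immunological response rate for the selected optimal dose of INO-4700".

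Placebo does enter the planned analyses. Responder percentages with Clopper-Pearson intervals are given within each group. In Part 2 the "binding antibody titer difference between INO-4700 and placebo will be analyzed using the geometric mean fold ratio", and neutralization and cellular response are compared by differences in medians. SAP 3.2 has active and placebo data pooled and summarized. Protocol 8.5.9 and SAP 3.6 allow optional logistic models. The responder differences that are specified, however, are between active groups only: "the difference in percentage of overall immune responders including seroconverters (i.e. positive titer) between all pairs of INO-4700 study groups".

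**The concern.** Read literally, the rule lets any upward movement between two noisy measurements make a responder, and the either/or structure gives each participant two chances. If every true responder is counted, chance increases can only add to the numerator.

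That would matter less if the criterion compared active with placebo, because both arms carry the same background. Here both 70% criteria take the active rate at face value. Meeting 70% would not show that 70% of participants responded to the vaccine.

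The endpoint is important: it is a stated minimum for advancing a regimen, and it is the only one with a formal hypothesis and a sample size (Protocol 8.6, SAP 3.1). A reader of the study report also needs the numeric rule to interpret any Week 10 response rate.

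**Working it through.** **Inputs from the documents.** Part 2: n = 260 evaluable active, p0 = 0.70, p1 = 0.80, one-sided alpha 0.025, stated power above 90% (Protocol 8.6, SAP 3.1). Part 1: 32 per active group; placebo groups F to I, 4 × 8 = 32 in total (Protocol Table 1).

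**The plan's own figure.** The smallest count c with P(X ≥ c | 260, 0.70) ≤ 0.025 is c = 197 (75.8%), with exact alpha 0.0232. Power at 0.80 is P(X ≥ 197 | 260, 0.80) = 0.960, so the stated power is confirmed.

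**Assumption.** Let r be the true vaccine-response rate and f the fraction of true non-responders who show an increase on either component. All true responders are taken to be counted. The documents give no value for f, so 0 to 20% is shown.

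- Observed rate: p = r + (1 − r)f.
- True rate behind an observed 70%: r = (0.70 − f)/(1 − f).
- Part 1 minimum: 22/32 = 68.8% fails and 23/32 = 71.9% passes, so P(pass) = P(X ≥ 23 | 32, p).
- Part 2 rejection: P(X ≥ 197 | 260, p).

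| f | True r when observed is 70% | p at r = 0.60 | P(pass Part 1) at r = 0.60 | p at r = 0.70 | P(reject Part 2) at r = 0.70 |
|---|---|---|---|---|---|
| 0 | 0.700 | 0.600 | 0.116 | 0.700 | 0.023 |
| 0.05 | 0.65/0.95 = 0.684 | 0.620 | 0.167 | 0.715 | 0.071 |
| 0.10 | 0.60/0.90 = 0.667 | 0.640 | 0.231 | 0.730 | 0.175 |
| 0.20 | 0.50/0.80 = 0.625 | 0.680 | 0.398 | 0.760 | 0.568 |

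**What f requires of each component.** If the two components are independent with chance q each, f = 1 − (1 − q)². Then f = 5, 10 and 20% need q of only 2.5, 5.1 and 10.6%.

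**Precision of the missing contrast.** Illustrative Newcombe 95% intervals for one active group against 32 pooled placebo participants:
- 22/32 v 6/32: difference 50 points (26 to 67), width 40.5.
- 22/32 v 10/32: 38 points (13 to 56), width 43.3.
- 23/32 v 16/32: 22 points (−2 to 43), width 44.4.

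**The case against.** **The placebo rate would be visible.** Within-group responder rates, the pooled summaries in SAP 3.2 and the optional logistic models would show the background rate to anyone who looks. This stands. The plan does not ignore placebo; what is missing is a specified active-minus-placebo responder difference and any use of it in the 70% criteria.

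**A cut-off may exist elsewhere.** Figure 3, which holds the dose-selection criteria, is not shown, and the Laboratory Manual is not among the documents. This stands as a limit on the point. Protocol 6.4.6 cites the manual for sample collection and shipment, however, and SAP 4.3.1, where a derivation would be expected, has none.

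**A positive titer in a naive population may mean negative-to-positive.** Exclusion criterion (g) removes people with prior MERS-CoV or camel exposure. This weakens the noise argument for the antibody component, but only in part: serology is at the investigator's discretion, positivity has no number, and the cellular component has no such qualifier.

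**The harm did not occur.** This also stands. The administrative memo that ended the trial after Part 1 cites "Week 10 interim immunology results, which did not meet the criteria for Part 2 dose selection". The Part 2 error rates describe a test that will not be run.

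**The report must already describe changes.** The SAP approval page says that changes to planned analyses will be described in the study report. That covers a departure from 6.4.6, but not a rule that 6.4.6 left unquantified.

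A reader might infer from the missed criteria, set against the 92% response after two 0.6 mg immunizations in Protocol 1.3.1, that a stricter rule was applied at Week 10. The documents do not support this. The 92% is an interim result from a 60-volunteer, three-regimen study; its arm size and responder rule are not given, and formulation, population and timing may differ. The memo gives no group rates, and the 8.5.6 criteria include the unseen Figure 3, so even the natural reading that all five groups fell below 70% is an inference.

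**Conclusion.** The point holds as a defect in the written endpoint and a gap in reporting. The visible definition is any increase on either component, without a cut-off or a deciding antibody assay, and both 70% criteria read the active rate alone. Under that rule the bias runs upward. At assumed false-increase fractions of 5, 10 and 20%, the rate is overstated by about 2 to 7.5 points at an observed 70%, the chance that a true-60% group meets the Part 1 minimum is up to about three times as high, and the Part 2 type I error would be 0.07, 0.175 or 0.57 instead of 0.023.

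These sizes rest on an assumed f and on no true responder being missed; the definitional gap rests on neither. A reader might conclude that the rule misled the sponsor. It did not produce a false advance, and because false responders push towards passing, they cannot account for the decision to drop Part 2.

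**What to change.** **Now, in the clinical study report.** State the numeric rule, the antibody assay and the visit behind the Week 10 responder rates (Part 1 also samples at Week 6), and say whether they differ from Protocol 6.4.6. For each active group, give the responder difference from pooled placebo with a 95% CI. This takes one paragraph and one table, with no new samples. With 32 pooled placebo participants the interval is wide, about 40 to 44 points in the examples.

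**If the design is reused.** In Protocol 6.4.6 and 8.5.2 and SAP 4.3.1:
- Name the deciding assays, and define response for each by a numeric rise over baseline set above that assay's validated variability. Take it from assay validation, not from this trial's placebo data.
- Add a rule for baseline-positive participants that still credits a sufficiently large rise.
- Report the active-minus-placebo responder difference with its 95% CI beside the 70% criterion, not as an extra test.
- Confirm that 70% is still the intended threshold under the numeric rule, since response rates may be lower.
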